4.3.4 Handling of Withdrawals

Participants will be asked to attend an exit visit in person to sign a withdrawal of consent form. Reasons for withdrawal will be detailed and recorded in the patients CRF by the RA. If participants are withdrawn from the study due to worsening of OCD symptoms (i.e. Y-BOCS \geq 32) or mood (medical monitor's decision in cases of \geq 24 SIGHD-17), referral back to their treating doctor for appropriate care will be advised. In cases of strong suicidal ideation/intent, the participant will be seen by one of the medical investigators of the study.

5 STUDY INTERVENTION/INVESTIGATIONAL PRODUCT

5.1 Study Product Description

5.1.1 Acquisition

NAC and placebo will be produced by Lipa Pharmaceuticals and both NAC and placebo will be supplied by Bioceuticals, in line with strict pharmaceutical Good Manufacturing Procedure (GMP).

5.1.2 Formulation, Packaging, and Labeling

Each opaque capsule will contain 500mg of NAC or microcelluose (placebo). The NAC and placebo capsules will be identical in colour, size and shape, and will be packaged in identical containers. Each container will contain 120 capsules. NAC has a strong sulfur odour, therefore, all IP will be contain a small sachet of NAC powder to mitigate any potential unblinding to the participant and RAs involved in assessments. An independent researcher will clearly label each participants IP series with a treatment number and best before date. The trial products will be stored in accordance with manufacturer's instructions which adopt Pharmaceutical Good Manufacturing Practice. Until dispensed to the participants, the IP will be stored in a securely locked area, only accessible to authorised personnel, in accordance with GCP drug storage requirements.

5.1.3 Product Storage and Stability

The IP will be kept in white, airtight containers and stored in a locked cupboard at each trial site. Participants will be advised to store their IP in a cool dry place and out of direct sunlight (below 25 °C).

5.2 Dosage, Preparation and Administration of Study Intervention/Investigational Product

All participants will commence the IP at a dose of two capsules, twice per day for the first eight weeks. The IP will be advised to be taken at least one hour away from other medications and after food, with water or orange juice and minimum of five hours between IP doses. All doses will be taken orally.

In cases of non-response (determined by < 35% reduction in Y-BOCS score from baseline), participants IP will be titrated by 500mg BID (1,000mg per day) from week-8, up to a maximum dose of 4,000mg per day (for example, see table 5.1 below). Note, participants may only increase their dose by 1,000mg per day and remain on this dose for the following four weeks before reassessing response and tolerance at the next study visit. If side effects are current/ongoing at a time point where titration may occur, for example, week-8, the medical investigators will determine if titration is appropriate for the participant. In the event that titration does occur, the RA will call the participant one week later to ensure tolerance to the higher dose. The medical investigators will be notified of any reported side effects and will determine if appropriate for the participant to continue on the titrated dose, or return to the previous tolerable amount.

Table 5.1 Example titration strategy of IP in cases of non-response* reported at each study visit

Visit period	Number of	Dose of IP/day	Containers
	capsules		required
Baseline → Week-4	2 BID	2,000mg	1 x 120c
Week-4 → Week-8	2 BID	2,000mg	1 x 120c
Week-8 → Week-12*	3 BID	3,000mg	2 x 120c
Week-12 → Week-16*	4 BID	4,000mg	2 x 120c
Week-16 → Week-20*	4 BID	4,000mg	2 x 120c

Note *In cases of non-response (<35% reduction in Y-BOCS score from baseline) participants may increase the dose of IP by 1,000mg per day from these time points. Conversely, participants may reduce the dose of IP in the event of intolerable side effects, as determined by the participant or medical investigators.

5.3 Accountability Procedures for the Study Intervention/Investigational Product(s)

The IP will be shipped from Bioceuticals HQ in QLD to the Melbourne and Brisbane study sites by Australia Post or Express Courier. The IP will be ordered in amounts sufficient to randomise 20 participants and a new order for 20 new participants will be placed when levels reach no lower than stock required to randomize five new participants. When stock arrives to the designated study site, an RA will check off each unit against an invoice provided by Bioceuticals. Received stock will be logged in a password protected recruitment and tracking excel spreadsheet as well as a drug accountability folder specific to each study site.

5.4 Assessment of Subject Compliance with Study Intervention/Investigational Product

Participants will be asked to return their IP container from the previous 4-weeks with any remaining capsules left inside at each follow-up visit. The RA will give the container to a third party who will count any remaining capsules and record the value into the participants CRF. The days since last visit will be determined and the expected amount of capsules to be taken by the participant during this time calculated, for example, 28 days x 6 capsules per day (3,000mg of IP) = 168 capsules. This value will be subtracted from the amount of capsules that were in the container upon dispensing, and compared with the amount of capsules returned by the participant to determine compliance.

5.5 Concomitant Medications/Treatments

Participants must be receiving treatment for their OCD (pharmacotherapy and/or psychological interventions) to be permitted eligible for the study (see table 5.2 for permitted medications). The dosages and duration of the medications below must be stable i.e. be employed for a minimum of 8-weeks at consistent dosages and within the recommended therapeutic range for OCD (as specified in table 5.2). If the participant is currently trialing their very first medication, 12-weeks will be considered stable. In cases where participants are taking doses of medications outside of these ranges, for example, escitalopram 60mg/day or an augmented medication below the dosage range, the medical investigator/s at the clinical trial site in question will determine if participation in the study is appropriate.

Table 5.2 Medications and therapies that are permitted during the study

Medication and therapeutic dosage range for OCD (mg/day)						
SSRIs		SNRIs/NaSSA/Other medications				
Fluoxetine	20-80mg	Venlafaxine	150-375mg			
Fluvoxamine	100-350mg	Desvenlafaxine	50-200mg			
Sertraline	50-200mg	Duloxetine	60-120mg			
Paroxetine	20-60mg	Mirtazapine	30-90mg			
Escitalopram	10-40mg	Agomelatine	25-50mg			
Citalopram	20-80mg					
Vortioxetine	10-30mg					
Antipsychotics		Glutamate modulating agents				
Risperidone	0.5mg-4mg	Memantine	5mg-20mg			
Aripiprazole	6mg-30mg	Topiramate	50-200mg			
Quetiapine	25mg-400mg	Lamotrigine	50-200mg			
Asenapine	5-20mg	TCA				
Lurasidone	40-120mg	Clomipramine	50-300mg			
Other						
Psychological	E.g. regular/consistent ERP, CBT					
interventions*	L.g. regular/consistent ERF, CD1					
Benzodiazepines*	Dose and frequency to be determined by medical monitors					

Note *Only when used as an adjunctive therapy (Bloch & Pittenger, 2014; Fornaro, 2011; Sansone & Sansone, 2011)

5.6 Advertising and enquires

The study may be advertised via the following mediums (where permitted)

- GP clinics & pharmacies affiliated with TONIC media (http://www.tonichealthmedia.com.au/)
 - Displaying of DL study brochures in health notice boards (O-NAC trifold DL brochure version 1)
 - Digital A3 image with study details displayed in health notice boards (see O-NAC A3 digital image version 1)
- Clinician referrals at TMC, RBWH and NICM
- Epworth Mental Health Clinic
- OCD Clinic Brisbane
- Anxiety House Brisbane
- St. Vincent's Hospital
- Facebook, Google and other social media advertising
- The Melbourne Clinic OCD in-patient program
- Swinburne University and other University psychology clinics
- Anxiety Recovery Centre Victoria
 - Seminars
 - Newsletters
 - Support groups
- A clinical trial recruitment company (e.g. TrialFacts)
- Community engagement including local GP offices, psychology practices, noticeboards and letterbox flyers
- Media releases and promotion including newspaper articles, radio interviews and television appearances

5.7 Pre-screening

Potential participants may enquire about the study via telephone or email, where an RA will explain the details of the study and answer any questions. If the person enquiring remains interested in the study, the RA will outline the information required to be gathered over the phone (e.g. age, medical history, current medication, history and current presentation of their OCD) to determine if the person meets general eligibility for the study. If they wish to continue with the specified pre-screening questions (by providing verbal consent), the RA will ask for the person's name, age, current medications, mental health diagnoses, medical history, brief treatment history and presenting symptoms. If they appear eligible after questioning, the PICF for the study will be sent and the person encouraged to read thoroughly and discuss the details with their treating doctor. A follow-up call will be made by the RA to assess interest and if willing, a baseline screening session will be made for the individual. Alternatively, enquiring individuals may complete an online pre-screening questionnaire (facilitated by REDCap software) which will ascertain similar information (see appendix for a copy of the REDCap pre-screening questionnaire and section 11.3.1 regarding REDCap confidentiality). Study staff will be notified by automated emails from REDCap when a pre-screening questionnaire is completed. A follow-up phone call will be made by the RA to clarify any necessary details highlighted in the questionnaire and let the person know if they are eligible to proceed with the study procedures. If so, the PICF will be sent and baseline booked as outlined above.

In cases where strong suicidal ideation or distress is apparent in people enquiring over the phone, the RA will encourage the person the make immediate contact with their treating doctor or psychologist or present to their nearest ER, by calling 000 if necessary. If necessary, RA's will contact emergency services if any safety concerns are voiced over the phone or if the RA is concerned about the welfare of any potential/current participants.

5.8 Baseline 1 session

Individuals that attend the baseline 1 session will meet with an RA who will discuss the PICF for the research study. An opportunity will be provided for the individual to ask any questions or raise any queries before signing the consent form. Consenting participants will be asked to provide demographic information, current and previous medications, a medical history as well as caffeine,

alcohol and drug intake over the last 3-months. A detailed description of the participants OCD, and any co-morbid mental health conditions, will be asked including its suspected onset, time of diagnosis, presentation and treatments employed since its occurrence. The Y-BOCS symptom checklist will then be administrated by the RA to determine the participant's current and most prominent obsessive and compulsive symptoms, as well as identifying symptoms experienced previously. The RA will then administer the Y-BOCS severity scale (based on the most prominent symptoms identified on symptom checklist) to ascertain the current severity of the OCD and determine eligibility. If eligible (scoring ≥16 and ≤31 on the Y-BOCS), the RA will administer the Y-BOCS question 11 to determine the participant's insight regarding their OCD symptoms, followed by the SIGHD-17. In cases where individuals do not meet me the inclusion criterial for the study, they will be outlined the reasons why and reimbursed \$20 for their time. Referral to appropriate treatment will be advised where necessary, for example, back to their treating doctor or OCD support groups such as ARCVic. If the individual does meet eligibility criteria for the study thus far, they will be asked to complete the DOCS, BAI, BIS-11, SDS, PGI-S and WHOQOL-BREF. Participants may complete these self-reporting questionnaires on site or, if preferred, they may be taken home to complete. An appointment will be made to attend the baseline 2 session to complete remaining screening assessments and return completed self-reported questionnaires (if applicable). This appointment will ideally take place within the next 7 days where possible, however, if 7+ days later, the Y-BOCS will be re-administrated at the start of the baseline 2 session to re-assess eligibility.

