Description of Agent: N-acetylcysteine (NAC) is an acetylated form of the essential amino acid cysteine. NAC possess glutamate modulating activity and is the rate limiting substrate for glutathione (GSH) production, a potent endogenous antioxidant. Participants will take NAC or matching placebo (capsule form) orally in doses between 2,000mg – 4,000mg per day, depending on individual treatment response.

Description of Study Design: 20 week, randomised, double blind placebo controlled trial with a 4-week, single blinded, placebo run out

Estimated Time to Complete Enrollment: 3.5 years

Schematic of Study Design:

Assessment Schedule

	Baseline 1	Baseline 2	W4	W8	W12	W16	W20	W24
PICF	Х							
Demographics	Х							
Medical hx	Х							
Treatment hx/review	Х	Х	Х	Х	Х	Х	Х	Х
Caffeine, drug &								
alcohol intake	X		X	Х	Х	Х	X	X
Blood pressure		Х	Х	Х	Х	Х	Х	Х
NetSCID-5		Х						
Qualitative review			Х	Х	Х	Х	Х	Х
Y-BOCS sx checklist	Х	X*	Х	Х	Х	Х	Х	Х
Y-BOCS	Х	X*	Х	Х	Х	Х	Х	Х
DOCS	Х		Х	Х	Х	Х	Х	Х
SIGHD-17	Х		Х	Х	Х	Х	Х	Х
BIS-11	Х							

	Baseline 1	Baseline 2	W4	W8	W12	W16	W20	W24
BAI	Х		Х	Х	Х	Х	Х	Х
SDS	Х		Х	Х	Х	Х	х	Х
WHOQOL-BREF	Х				Х		х	
DQES v3.2		Х						
CGI-I			Х	Х	Х	Х	Х	Х
CGI-S		Х	Х	Х	Х	Х	Х	Х
PGI-S	Х		Х	Х	Х	Х	Х	Х
PGI-I			Х	Х	Х	Х	Х	Х
SAFTEE			Х	Х	Х	Х	Х	х
ВМІ		Х						
Blood collection		X**						

^{*}The Y-BOCS will be administered at baseline 2 if this appointment occurs more than seven days after baseline I visit **completed at any time point before conclusion of the study

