4.2 Subject Exclusion Criteria

Participants will be excluded from the study in the event of:

- Bipolar disorder*a
- Psychotic disorders*a
- Primary diagnosis of Obsessive-compulsive spectrum disorders including hoarding, body dysmorphic disorder, trichotillomania (secondary diagnosis permitted)
- Severe depression (as defined by HAM-D score of ≥24)
- Alcohol/substance abuse*
- Y-BOCS score of ≥32 (extreme OCD)
- Treatment refractory OCD (see Figure 4.1)

• Currently engaging in intensive psychological therapies for OCD (a 4-week washout will be required before reassessing eligibility), for example:

- o In-patient OCD programs
- Intensive out-patient programs, for example 15-17 CBT sessions (involving ERP) conducted by a clinician within a 4-8 week period as outlined by Franklin,
 Abramowitz, Kozak, Levitt, & Foa, 2000; Simpson et al., 2013; Simpson et al., 2008
- Online CBT courses, for example, 'This Way Up' or STOP by Swinburne University
- Medications with known or suspected negative interactions with NAC (see Table 4.2 for guidelines) as determined by the medical investigator/s

Table 4.2 Therapeutic agents that may interact with NAC

		Strength of	Evidence
Agent	Mechanism	interaction	level
Activated charcoal	Strongly binds to up to 96% of orally ingested	Moderate	Clinical
Activated charcoal	NAC (dose dependent)	Moderate	studies
Nitro-glycerine	NAC potentiates the activity of nitro-glycerine	Major	Clinical
Twitto grycerine	and causes hypotension	Wajoi	studies
Insulin (inhaled	NAC (inhalation preparations) may affect		Theoretical, -
preparations)	absorption of rapid acting insulin when taken	Moderate	based on
proparations)	concurrently.		pharmacology
Chloroquine	NAC may prevent the build-up of heme inside	Moderate	In vitro or
(Aralen)	cells and thus reduce Aralen's efficacy	Woderate	animal study
>200mcg selenium	Selenium is required for GSH production and	Moderate	In vitro or
2200mog colomani	thus, may confound NAC activity	Wodorato	animal study
Anti-coagulant/anti-	NAC may slow blood clotting (via nitric oxide		In vitro or
platelet medication	activity) and therefore, potentiate the effects	Moderate	animal study
platelet mealeation	of these medications		aa. stady
	NAC may lower blood pressure via GSH's		
Blood pressure	influence on nitric oxide activity. Further,	Moderate	In vitro or
medication	NAC may potentiate hypotensive effects of	ouorato	animal study
	ACE inhibitors		

O-NAC Protocol

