6.2.5 Structured interview guide for the HAM-D, 17 item (SIGHD-17)

The HAM-D is a 17-item, multidimensional scale designed for clinicians to administer and has been used extensively in clinical trial research (including OCD studies) since the 1960s to assess intervention efficacy (Baer & Blais, 2010; Moritz, Meier, Hand, Schick, & Jahn, 2004). Each item explores common features of depression including depressed mood, feelings of guilt, suicidality, somatic and psychological anxiety and sleep (onset, maintenance early morning wakening). Both the impact and frequency of each item is investigated over the previous 7-day period and a score rated on a Likert scale (ranging from 0-4 for most items) with larger magnitudes correlating with greater severity. Internal consistency appears to be greater when using the structured guidelines for the HAM-D (Williams, 1988), thus, the structured HAM-D (17-tem) will be employed in this study. Inter-rater reliability is high for the HAM-D total score (0.80-0.98), despite being poor for some of its individual items in some instances (Bagby, Ryder, Schuller, & Marshall, 2004). Suggested severities of depression as per the total HAM-D score (17-item) include no depression (0-7); mild depression (8-16); moderate depression (17-23); and severe depression (≥24) (Zimmerman, Martinez, Young, Chelminski, & Dalrymple, 2013).

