7.1.3 Screening for suicidality

Suicidality is screened by item-3 of the SIGHD-17 at each study visit (with the exception of the initial baseline 2 session, where the SCID-CT-5 will be used). Participants are also asked at the beginning of each follow-up visit regarding worsening of mood, OCD symptoms, thoughts of self-harm and suicidal ideation. Participants will be withdrawn from the study if item-3 on the SIGHD-17 is equal to or greater than 3 and if not at immediate risk, will be advised to make contact with their treating doctor. In cases of strong suicidal ideation and intent (for example, SIGHD-17 item-3 score of 4), the participant will be asked to wait with the RA until a risk assessment can be conducted by one of the medical investigators on site. If necessary, the participant will be directed to emergency services or 000 will be called for immediate transfer. The participants treating psychiatrist or physician will be contacted immediately.

7.1.4 Procedures to be followed in the Event of Abnormal Laboratory Test Values or Abnormal Clinical Findings

In the event of high or low blood pressure (see table 6.1), participants will be asked to have their BP taken again by the RA before completion of the study visit. Recent intake of caffeine, alcohol, medication and cigarettes, exposure to cold temperatures as well as recent stressors, or feelings or stress will be ascertained. If the 2nd reading appears abnormal, they will be advised to see their GP or treating doctor.

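### After a delayed baseline 2 the protocol re-checks the Y-BOCS entry score but not the SIGHD-17, and leaves two possible reference scores for the titration and deterioration rules

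*Protocol*

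**What the plan says.** Screening is split over two visits, and investigational product is handed out at the end of the second (Protocol 5.9). On the gap between them, section 5.8 states an aim only: "This appointment will ideally take place within the next 7 days where possible". It continues: "however, if 7+ days later, the Y-BOCS will be re-administrated at the start of the baseline 2 session to re-assess eligibility". The footnote to the Assessment Schedule in the Protocol Summary words the trigger differently: "The Y-BOCS will be administered at baseline 2 if this appointment occurs more than seven days after baseline I visit". That footnote marks the Y-BOCS severity scale and its symptom checklist, and no other outcome scale. Section 3.2.1 also uses a more-than-7-days trigger.

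The exclusion list in 4.2 includes "Severe depression (as defined by HAM-D score of ≥24". The SIGHD-17, which supplies that score, is scheduled at baseline 1 and next at week 4. Section 7.1.3 confirms that it is not given at baseline 2: item 3 screens for suicidality at each visit "with the exception of the initial baseline 2 session, where the SCID-CT-5 will be used". Section 6.2.5 gives the recall period: "Both the impact and frequency of each item is investigated over the previous 7-day period". Section 6.2.2 gives the same seven days for the Y-BOCS.

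Two rules applied by site staff use a Y-BOCS baseline. In 5.2, non-response, which leads to titration, is "determined by < 35% reduction in Y-BOCS score from baseline". In 4.3.3, research assistants notify the medical monitors of a rise of more than 35% from baseline. Neither says which pre-treatment score is meant when there are two.

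**The concern.** The trial has two numeric entry scores, the Y-BOCS (16 to 31) and the SIGHD-17 (below 24), and both look back seven days. Once more than seven days have passed, the protocol treats the first as needing a fresh check before dosing and leaves the second alone. A participant whose SIGHD-17 has since reached 24 can be enrolled with every written step followed. The next SIGHD-17 is at week 4, after four weeks of investigational product.

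The second problem arises in the same participants. The repeat Y-BOCS is described only as an eligibility check, so its role as a reference value is left open. Two research assistants applying the 35% rules in good faith could use different scores, and the same participant would then be handled differently at different sites.

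**Working it through.** The plan states no figure on this point to reproduce. The check is textual, with arithmetic for the consequence.

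**1. The two entry scores after a delay of more than seven days**

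| | Y-BOCS | SIGHD-17 |
|---|---|---|
| Numeric entry limit | 16 to 31 (4.1, 4.2) | 24 or more excluded (4.2) |
| Recall | 7 days (6.2.2) | 7 days (6.2.5) |
| Taken at baseline 1 | yes | yes |
| Repeated at delayed baseline 2 | yes (5.8, schedule) | no (schedule, 7.1.3) |
| Upper limit on age at first dose | about 7 days, by the repeat | none stated |

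The NetSCID at baseline 2 covers mood disorders (6.1) and suicidality (7.1.3), but yields diagnoses and not a SIGHD-17 total. It cannot show whether the participant is now at 24 or above.

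**2. The trigger.** On its face, 5.8 requires a repeat on day 7 itself. The schedule footnote and 3.2.1 require it only from day 8. The difference is one day, but the passages disagree.

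**3. The titration rule under two candidate baselines.** The scores are assumed, since the protocol gives no retest data. Percentage reduction = (baseline − follow-up) / baseline.

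- Baseline 1 = 28, baseline 2 = 22, week 8 = 17.
- From the first: (28 − 17) / 28 = 39.3%, a response.
- From the second: (22 − 17) / 22 = 22.7%, a non-response.

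In general, a participant responds if the follow-up score is at most 0.65 × baseline:

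| Two baselines | Response cut-offs | Follow-up scores that change status |
|---|---|---|
| 28 and 22 | 18.2 and 14.3 | 15 to 18 |
| 28 and 24 | 18.2 and 15.6 | 16 to 18 |
| 31 and 27 | 20.15 and 17.55 | 18 to 20 |
| 26 and 24 | 16.9 and 15.6 | 16 only |

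**4. The deterioration rule.** Notification is due if the score exceeds 1.35 × baseline. Section 4.3.3 separately lists a Y-BOCS of 32 or more as a withdrawal criterion.

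- At baseline 24 the trigger is 1.35 × 24 = 32.4, so the 32 criterion is reached first. The same holds for any higher baseline.
- At lower baselines the choice matters. With 22 and 18 the triggers are 29.7 and 24.3, so scores of 25 to 29 change status.

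**The case against.** Four points on the other side carry weight.

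- **Depression is assessed before dosing.** A reader might infer that a severely depressed participant could start treatment with nobody having looked. The documents do not support that. The NetSCID is done at baseline 2 before dispensing, covers mood disorders and suicidality, and can lead to exclusion; treatment is also reviewed at that visit. What remains is that the numeric criterion is not re-checked.
- **The secondary baselines are less exposed than they look.** A reader might infer that most of them are of unlimited age. The self-report forms may be taken home and returned at baseline 2 (5.8, 5.9), so they may be completed close to first dose. The DOCS covers the past month and the WHOQOL-BREF four weeks, so a short delay hardly dates them. The seven-day argument fits the SIGHD-17 firmly and the BAI in part.
- **The analysis baseline belongs to the SAP.** Which Y-BOCS enters the model is commonly settled there, and its absence from the protocol is no finding. This does not dispose of titration and notification, which sites apply during conduct.
- **The size is uncertain.** The protocol aims for seven days, allows for both sessions on one day (2.3.2, 5.10), and gives no rate of delay. The six-point fall in the worked case is twice the 3-point effect in section 8.1; with a two-point gap (26 and 24) only one follow-up score changes status. For the SIGHD-17, an assumed change SD of 3 to 5 points with no mean drift would give someone at 22 a 31–38% chance of scoring 24 or more on repeat. But that SD comes from no document, and such retest noise would also occur within the accepted seven days, so the figure does not measure harm from delay.

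**Conclusion.** The point stands in a limited form. When baseline 2 is delayed beyond seven days, one of two numeric entry scores with the same recall period is refreshed before dosing and the other is not. The instrument used in its place does not produce the score on which the exclusion depends. In the same participants, the titration and notification rules have two possible reference values, and the trigger for the repeat is worded inconsistently.

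The size cannot be fixed from the documents. It depends on how many participants are delayed and how far their scores move, and neither is given. Under the assumed pairs of scores, one to four follow-up values change titration status. For notification, the choice adds nothing when both baselines are 24 or higher, because the criterion of 32 or more is reached first.

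A reader might also infer that the treatment comparison is biased. It is not on this account: both Y-BOCS scores precede treatment and neither favours an arm. The consequence is noise and uneven conduct in an unknown subset, which makes this a worthwhile, inexpensive improvement and not a threat to the trial's conclusion.

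**What to change.** 1. Apply the existing seven-day trigger to the SIGHD-17 at baseline 2 and re-apply the existing exclusion before dispensing. Amend 5.8, 5.9, the Assessment Schedule and its footnote, and the exception in 7.1.3 to match. The BAI could be repeated under the same trigger, as it also has a seven-day recall; this is optional.
2. Word the trigger identically in 5.8, 3.2.1 and the schedule footnote, so that day 7 is handled one way.
3. Reconcile 3.2.1, 4.3.3, 5.2 and 5.8 so that every site applies one stated reference Y-BOCS in the titration and notification rules. Which score that should be is for the investigators and is not proposed here.

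The cost is one further short interview (and one questionnaire if the BAI is added) and probably a few more screen failures, among delayed participants only. Items 2 and 3 need wording alone.
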